1.9 DEFINITION OF THE SAFETY VARIABLES

- Occurrence of adverse event
- Occurrence of serious adverse event

1.10 ANALYSIS PRINCIPLES FOR FINAL ANALYSIS

- All analyses will be conducted on an ‘intention-to-treat’ basis, defined as follows:
 - All patients who enter at least one VAS score for muscle symptoms during a statin period and at least one VAS score for muscle symptoms during a placebo period will be included in the final primary analysis.
 - For analyses of secondary outcomes from the patient questionnaire (single monthly measurement), analyses will include all patients who complete at least one measure during a statin period and at least one measure during a placebo period.
 - Periods of allocation to statin will be compared to periods of allocation to placebo, irrespective of adherence to the allocated treatment.
- All statistical tests will be two-sided, and the nominal level of α will be 5%. Confidence intervals for the primary outcome will be set at the 95% level.
- P values will not be adjusted for multiplicity. However, the outcomes are clearly categorised by degree of importance (primary and secondary). Confidence intervals for secondary outcomes will be set at the 99% level.
- The primary analysis will not impute missing values. Where the number of missing observations is substantial, we will report the number of observations used in the analysis. Robustness of conclusions to missing data will be explored via sensitivity analysis.
- Analyses exploring the effect of adherence on primary and secondary outcomes will be undertaken as secondary analyses.
- All adverse events will be coded using MedDRA Version 19.1.

1.11 INTERIM ANALYSES

Statins are widely used already. The primary outcome is itself a side effect. Despite this relatively low-risk setting, an independent DMC has been appointed for this trial to oversee the safety monitoring. The DMC will review on a regular basis accumulating data from the ongoing trial and advise the Trial Steering Committee regarding the continuing safety of current participants and those yet to be recruited, as well as reviewing the validity and scientific merit of the trial.

The DMC composition, name, title and address of the chairman and of each member, are in the DMC Charter. Membership includes expertise in the relevant field of study, statistics and research study design. The DMC Charter includes, but is not limited to, defining:

- (a) the schedule and format of the DMC meetings
- (b) the format for presentation of data
- (c) the method and timing of providing interim reports
- (d) stopping rules

Standard Operating Procedures: The Data Monitoring Committee (DMC) has the responsibility for deciding whether, while randomisation is in progress, the unblinded results (or the unblinded results for a particular subgroup), should be revealed to the TSC. The DMC Charter states that they will do this if, and only if, two conditions are satisfied:

(1) The results provide proof beyond reasonable doubt that treatment is on balance either definitely harmful or definitely favourable for all, or for a particular category of, participants in terms of the major outcome;

(2) The results, if revealed, would be expected to substantially change the prescribing patterns of clinicians who are already familiar with any other trial results that exist. Exact criteria for “proof beyond reasonable doubt” are not, and cannot be, specified by a purely mathematical stopping rule, but they are strongly influenced by such rules. The DMC Charter is in agreement with the Peto-Haybittle stopping rule whereby an interim analysis of major endpoint would generally need to involve a difference between treatment and control of at least three standard errors to justify premature disclosure. An interim subgroup analysis would, of course, have to be even more extreme to justify disclosure. This rule has the advantage that the exact number and timing of interim analyses need not be pre-specified. In summary, the stopping rules require extreme differences to justify premature disclosure and involve an appropriate combination of mathematical stopping rules and scientific judgment.

1.12 CONSENT-RELATED ISSUES

A patient is free to change their minds about participation at any time. If consent for use of data is withheld, data collected to the point of withdrawal of consent will be used as part of the intention to treat analysis. All relevant adverse events identified will be reported as required to all relevant authorities and included in the safety analysis.

2 STATISTICAL ANALYSIS

2.1 TRIAL PROFILE

Flow of patients through the study will be displayed in a CENT (CONSORT extension for reporting N-of-1 trials) flow diagram. We will report the number of screened patients who met study inclusion criteria and the number included and reasons for exclusion of non-included patients. Numbers allocated to each randomized sequence will be summarised by frequencies and percentages.

Additionally, for interim analyses only, recruitment will be summarised by graphs of patient and GP recruitment over time, and frequencies of patients recruited by GP practice.

2.2 BASELINE CHARACTERISTICS OF PATIENTS

Baseline characteristics of participants will be described overall. Discrete variables will be summarised by frequencies and percentages. Percentages will be calculated according to the number of patients for whom data are available. Where values are missing, the denominator (which is less than the number of patients assigned to the treatment group) will be stated in either the body or footnote of the corresponding summary table. Continuous variables will be summarised using standard measures of central tendency and dispersion, i.e. mean and SD, or median and 25th, 75th percentiles.

Study procedures, including participation in the voluntary genetic sub-study and choice of method for primary outcome data collection, will be described overall as for baseline participant characteristics.

2.3 DESCRIPTION OF ANALYSES

2.3.1 PRIMARY OUTCOME

Medians and 25th, 75th percentiles, or mean and SD, as appropriate, of the average VAS daily muscle symptom scores will be reported separately for the six placebo and statin periods, along with summaries of the paired differences (statin-placebo within paired treatment blocks). Trajectory plots will be made for individual patients, and for all patients together grouped by allocated sequence. Numbers of missing measurements will be tabulated by period and allocated treatment.

The overall effect of statin on muscle symptoms, as measured by self-report VAS pain scores, will be estimated by a mean difference (statin – placebo) with a 95% confidence interval (CI). This will be obtained from a linear mixed model with a random participant effect, and allowing the treatment effect to vary by participant (i.e. the model will include both a fixed and random treatment effect, with an unstructured covariance matrix between the two random effects). Residual errors will be modelled using a first-order auto-regressive error structure across all trial days for each person to account for correlation between the 7 daily measurements (i.e. an order auto-regressive error structure with “days under treatment in the trial” as the timescale; noting that each period is exactly 56 days), with robust standard errors to account for non-normality of the VAS scores. In the event of model convergence problems (which may occur if patients report few of the 7 daily VAS scores), the auto-regressive structure will be omitted and robust standard errors used.

The mixed model will be fitted via maximum likelihood. A likelihood ratio test will be used as the test of statistical significance of statin allocation versus placebo on VAS muscle symptom scores.

2.3.2 SECONDARY OUTCOMES

Descriptive analyses of muscle symptoms

Details of symptoms experienced (whether the patient believes they were caused by the study medication, the site, the extent to which the pain impacts on other aspect of life, other symptoms experienced) will be reported for all periods in which the patient reports experiencing muscle symptoms. For these descriptions, the denominator will be the number of periods in which symptoms are experienced; no attempt will be made to account for the clustering by patient. These descriptive statistics will be repeated splitting by treatment actually received.

Descriptions of symptoms experienced will also be made using the patient as the unit of analysis. For these descriptions, patient-level variables for patients who report one or more period where they experienced muscle symptoms will be defined as follows: (i) a new location variable: always multiple sites/sometimes multiple sometimes single/always single site, (ii) four new site variables indicating symptoms ever experienced in head/neck versus not, etc., and (iii) mean VAS score for impacts on other aspects of life across periods in which symptoms were experienced by that patient.

Because these descriptive statistics do not respect the randomised allocation of treatment, no comparisons between treatment groups will be made; no formal statistical inference will be undertaken.

Randomised comparisons of muscle symptoms experienced

The patient questionnaire collects a binary measure of whether the patient experienced muscle symptom or not during that treatment period. This binary measure will be compared between randomized treatment groups (statin – placebo) with an odds ratio and confidence interval, obtained using a logistic mixed model with random participant and random treatment effects with an unstructured covariance matrix between random effects.

As a more specific measure, a single binary outcome of whether the participant reports having muscle symptoms that they believe to be caused by the study medication will be derived (taking the values one if the participant reports symptoms and that they believe these are – or they don't know whether they are – related to the study medication, and zero if either the participant has no symptoms or the participant has symptoms but does not believe these are related to the study medication). This binary measure will be analysed as described in the previous paragraph.

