2.11 ADVERSE EVENTS

Reporting of Adverse Events for this trial: Atorvastatin is not a new drug and has a well-documented safety profile. Furthermore, this trial is being conducted in a population in which statin use is clinically indicated. It is anticipated that patients in this trial are at higher risk of cardiovascular diseases because of underlying clinical conditions requiring statin use. Additionally, as participation is for 15 months it is likely that they will have common medical problems (e.g. colds, coughs, fevers etc). On the basis that patients: (1) would have had prior exposure to the trial treatment, (2) the trial treatment is clinically indicated for their medical condition, and (3) the known safety profile of the trial treatment, we will limit adverse events to be reported to those events that fulfill the Serious Adverse Event (SAE) criteria as described below.

Patient Self-report: In the two-monthly questionnaire, patients will be asked to self-report any event which resulted in unplanned hospital admissions. Where a patient indicates that there was an unplanned admission, the GP/Research Nurse will be asked to submit a brief report to the CTU.

General Practitioner report: Participating GPs will report any event to the CTU that fulfill the Serious Adverse Event (SAE) criteria as described below within 24 hours of becoming aware of the event. To minimize the risk of unreported events, at two-monthly intervals, the Research Nurse/GP will conduct a search of their database for any StatinWISE patients who have been recorded as having died.

Definitions:

Adverse Event (AE): Any untoward medical occurrence not listed in the Investigational Medicinal Product Dossier (IMPD) and /or Summary of Product Characteristics (SmPC) affecting a trial participant during the course of a clinical trial.

Serious Adverse Event (SAE): A serious adverse event (experience) is an adverse event (as defined above) which at any dose:

- results in death
- is life-threatening
- requires inpatient hospitalisation or prolongation of existing hospitalisation; or
- results in persistent or significant disability/incapacity
- is a congenital anomaly/birth defect

Adverse Reaction (AR): An AE when there is at least a possibility that it is causally linked to a trial drug or intervention.

Serious Adverse Reaction (SAR): SAE that is thought to be causally linked to a trial drug or intervention.

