2.13 OUTCOME MEASURES

Primary outcome: The primary outcome is self-reported 'muscle symptoms', defined as pain, weakness, tenderness, stiffness or cramp to the body of any intensity, recorded where the participant believes they are associated with the study medication; these are the symptoms most commonly reported by patients and are often the reasons for discontinuation. The primary outcome will be assessed by the mean difference in VAS scores (range 0 to 100) between treatment periods with the trial treatment and treatment periods with placebo, estimated via a linear mixed model.

Secondary outcomes: Secondary outcomes relating to participant belief about the cause of their muscle symptoms, the site of muscle symptoms, how the muscle symptoms affected the participant and information about any other symptoms will be collected on the last day of each two-month treatment period, using a questionnaire (Appendix 5). The other secondary outcomes are adherence

to medication, the participant's decision about statin treatment following the trial, and whether they found their own trial result helpful.

Specifically, secondary outcomes will be:

1. The proportion of patients with muscle symptoms during each two-month period who report that they believe their symptoms were caused by the study medication, comparing periods of IMP treatment with placebo.
2. Site of muscle symptoms (single or multiple; head and neck/upper limbs/lower limbs/trunk).
3. Among patients reporting muscle symptoms, the difference in mean VAS scores (range 0 to 100) for the following, comparing periods of IMP treatment with placebo:
 - a. General activity
 - b. Mood
 - c. Walking ability
 - d. Normal work (includes both work outside the home and housework)
 - e. Relations with other people
 - f. Sleep
 - g. Enjoyment of life
4. Other symptoms that the patient believes can be attributed to the study medication (grouped: musculoskeletal; gastrointestinal; respiratory; neurological; psychological; other).
5. Adherence to study medication as assessed by: (a) self-report and (b) counting pills remaining in returned packages, and the relationship between adherence and muscle symptoms.
6. Participant decision regarding future statin use and the relationship to their primary outcome.
7. Whether patients found their own trial result helpful in making the decision about future statin use.

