2.17 ANALYSIS

Individual N-of-1 trials: The purpose of these analyses is to inform the individual patient of the effect of the IMP on their VAS muscle symptom score. The analysis and presentation of individual level results will be developed in collaboration with the Patient and Public Involvement (PPI) group. We will examine a range of graphical summaries and statistical analyses in order to identify the most informative presentation of individual results. As a result of this process, at the end of each individual trial the participant will be shown numerical and graphical summaries of their individual data, in relation to their IMP and placebo periods.

Combined analysis of N-of-1 trials

Primary analysis: To estimate the population average estimate of the trial treatment n VAS muscle symptom score, data from each N-of-1 trial will be aggregated to form a powerful dataset. We will adopt an intention-to-treat approach. Patients who enter data on muscle symptoms at least once during a treatment period with the IMP and at least once during a treatment period with placebo will be included in the primary analysis.

The primary analysis will be a linear mixed model for VAS muscle symptom score with random effects for participant and treatment and fixed period effects. Residual errors will be modelled using

a first-order auto-regressive error structure within each treatment period to account for correlation between the 7 daily measurements, with robust standard errors to account for non-normality of the VAS scores. Although VAS muscle symptom scores are unlikely to be exactly normally distributed, analysing such data using normal-based methods is likely to be a sufficiently robust approach.²⁶ All tests will be two-sided. $p < 0.05$ will be considered statistically significant.

Secondary analyses: Secondary outcomes relating to the impact of the IMP on other aspects of life will be analysed in a similar manner to the primary outcome, omitting the auto-regressive correlation structure since these secondary outcomes are measured once per treatment period. We will investigate whether the excess muscle symptoms, if any, experienced during treatment periods with the IMP appears to be concentrated in multiple sites.

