[figure not shown]
4. *(appears if the participant ticks yes for Question 1):* Indicate with a cross (x) on the scale the number that describes how, during the last two months, pain has interfered with your:

- General activity
- Mood
- Walking ability
- Normal work (includes both work outside the home and housework)
- Relations with other people
- Sleep
- Enjoyment of life

For each of (a) to (g), the following scale will appear:

5. (appears if the participant ticks yes for Question 1): **On the diagram, tap to highlight the area that hurts the most.**
(Paper form will read: 'On the diagram, put an X on the area that hurts the most.')

More than one area

The body will be divided into the following locations and answers should be categorized depending where the participant taps. For paper forms, the location given by X marked on the body will be entered into the web or app version at data entry. Locations: head and neck/upper limbs/lower limbs/trunk.

6. (All participants): **In the last two months, have you experienced any other symptom that you think is associated with your study medication?**

Yes (please specify)
(free text)
 No
 Don't know

PART 3: ADVERSE EVENTS

1. (All participants): **Have you been admitted to hospital in the last two months?**

Yes
 No

[figure not shown]
[figure not shown]
2. (Appears if the participant ticks yes for Question 1): **What was the reason for your admission to hospital?**

[figure not shown]
[figure not shown]
[figure not shown]
[figure not shown]
(free text)

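### SAP 2.3.2 summarises other attributed symptoms only for periods with muscle symptoms, although every participant is asked about them in every period

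*SAP*

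**What the plan says.** Protocol 2.13 lists as secondary outcome 4: "Other symptoms that the patient believes can be attributed to the study medication", in six groups. SAP 1.1(d) and 1.8 repeat it, and SAP 1.8 has it collected at the end of each of the six periods. None of these places limits it to periods with muscle symptoms. In SAP 1.8 that limit is stated for the seven impact scores only.

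In the patient questionnaire (Protocol Appendix 4, Part 2), item 6 is marked for all participants: "have you experienced any other symptom that you think is associated with your study medication". The possible answers are yes with free text, no, and don't know. Items 2, 4 and 5 appear only after a yes to the muscle-symptom question, and item 3 only after a no to item 2.

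SAP 2.3.2, under the descriptive analyses of muscle symptoms, covers attribution, site, impact and other symptoms together. It ends the list with "other symptoms experienced) will be reported for all periods in which the patient reports experiencing muscle symptoms" and adds that "the denominator will be the number of periods in which symptoms are experienced". Then: "These descriptive statistics will be repeated splitting by treatment actually received". It closes by saying that "no comparisons between treatment groups will be made; no formal statistical inference will be undertaken".

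On site of symptoms, Protocol 2.17 says the trial will look into whether any excess of muscle symptoms on the IMP "appears to be concentrated in multiple sites".

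**The concern.** An outcome asked of everyone is summarised only in a subset of periods, and that subset is defined by the trial's own main outcome, measured after randomisation. A participant who attributes nausea to the capsules but has no muscle symptoms in that period appears in no planned table.

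This matters because little else in the trial would record such a symptom. Protocol 2.11 says "we will limit adverse events to be reported to those events that fulfill the Serious Adverse Event (SAE) criteria", and questionnaire Part 3 asks only about hospital admission. Item 6 is the one question put to participants each period that invites non-serious, non-muscle complaints. The baseline form records headache, digestive problems, tiredness and feeling sick attributed to past statin use, so the trial treats them as relevant.

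**Working it through.** The documents give no figure on this point, so there is nothing to reproduce. The check is a comparison of the texts, then simple arithmetic on size.

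**1. Is there any other analysis of item 6?**

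- The randomised comparisons in SAP 2.3.2 cover any muscle symptoms, muscle symptoms attributed to study medication, a modified daily VAS score, and the seven impact scores. Other symptoms are not among them.
- The patient-level descriptions in SAP 2.3.2 are limited to patients with at least one muscle-symptom period. They cover location, site and impact, not other symptoms.
- SAP 1.10 admits patients with at least one statin and one placebo questionnaire measure, and compares periods by allocation. It decides which patients are included. It neither defines an analysis for this outcome nor lifts the restriction to certain periods.
- SAP 2.3.3 tabulates adverse events by allocation, but Protocol 2.11 limits reporting to events meeting the SAE criteria. Its adverse event definition also leaves out events already listed in the IMPD or SmPC, and the SmPC lists headache, nausea, dyspepsia and diarrhoea as common.
- Protocol 2.17 gives no analysis of this outcome.

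**2. How many questionnaires fall outside the summary?**

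Planned number: 200 patients (Protocol 2.1) x 6 periods = 1,200. With the 40% loss in Protocol 2.4: 200 x 0.6 = 120 patients, and 120 x 6 = 720 if nobody else returns any. Number left out = total x share of periods without muscle symptoms. That share is assumed.

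| Share of periods without muscle symptoms (assumed) | Left out of 1,200 | Left out of 720 |
|---|---|---|
| 30% | 360 | 216 |
| 50% | 600 | 360 |
| 70% | 840 | 504 |

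**3. What happens to counts, rates and differences?** Both cases use assumed rates.

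*Unrelated symptoms.* Take 600 periods per treatment, muscle symptoms in half of them, and other symptoms in 10% of statin and 5% of placebo periods regardless of muscle symptoms. All periods: 60/600 = 10% and 30/600 = 5%. Planned summary: 30/300 = 10% and 15/300 = 5%. The rates are right. The counts are halved, and 90 - 45 = 45 positive reports are missing.

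*Related symptoms.* Take muscle symptoms in 50% of periods on both treatments and other symptoms in 20% of those periods on both. In muscle-symptom-free periods, other symptoms occur in 10% on placebo and 20% on statin.

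- Placebo, all periods: 0.5 x 20% + 0.5 x 10% = 15%
- Statin, all periods: 0.5 x 20% + 0.5 x 20% = 20%
- All-period difference: 5 percentage points
- Planned summary: 20% - 20% = 0

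With muscle symptoms in 30% or 70% of periods, the all-period difference is 0.7 x 10 = 7 points or 0.3 x 10 = 3 points. The planned summary still shows 0.

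**4. Multiple sites.** Protocol 2.17 asks about the excess on the IMP, which is a treatment contrast. SAP 2.3.2 keeps site as a description by treatment received and bars comparison. SAP 2.3.8 lists two changes from the protocol, and this is not one of them.

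**The case against.** The best defence is that no treatment comparison of other symptoms was ever planned. In Protocol 2.13, outcomes 1 and 3 say that IMP and placebo periods will be compared; outcome 4 does not. The trial's aim is muscle symptoms, and the SAP admits that these descriptions do not respect randomisation and draws no inference from them. On this view the phrase in SAP 2.3.2 is a small drafting slip.

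Much of this stands. A reader might infer that the SAP silently dropped a promised randomised comparison of other symptoms; the documents do not support that. A reader might also infer that the rates must be biased. The first example above shows otherwise: bias needs a relation between the two kinds of symptom, which the documents neither show nor exclude. Nor are the data discarded, since nothing in the SAP deletes them. The multiple-site question is reduced to description rather than removed, and Protocol 2.17 commits to no particular model for it.

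The defence does not rescue the restriction. Even a purely descriptive report should cover the outcome as defined, and this wording is the only instruction an analyst has. The stated reason for barring comparison comes from selecting symptomatic periods and splitting by treatment received. Item 6 needs neither.

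**Conclusion.** The point holds as a mismatch between a secondary outcome defined for every period and a summary limited to muscle-symptom periods. Followed as written, the rule understates the count of other attributed symptoms whenever any are reported in a muscle-symptom-free period. Rates and differences are distorted only if other symptoms and muscle symptoms are related.

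The omission is 360-840 questionnaires with no loss to follow-up, or 216-504 under the 120-patient scenario. Both ranges rest on the assumed 30-70% share, and many of the omitted answers may be no. The primary analysis is unaffected. The SAP should be corrected before database lock.

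The multiple-site question is a separate and smaller matter: an undeclared step from investigating an excess on treatment to description alone.

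**What to change.** In SAP 2.3.2:

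- Take other symptoms out of the muscle-symptom descriptive block. Report item 6, as any symptom and by the six groups, over all completed questionnaires and by allocated treatment.
- As an addition beyond the protocol, compare any other attributed symptom by allocation, using the logistic mixed model already specified for the binary muscle-symptom outcome and the 99% interval that SAP 1.10 sets for secondary outcomes. State a rule for don't know. One option is the rule SAP 2.3.2 uses for its binary attribution outcome, which counts don't know as related. Leave rare groups descriptive.
- Define multiple-site muscle symptoms as yes or no in every period, with no symptoms coded no, and compare by allocation. This follows the SAP's own handling of the impact scores, which are set to zero in symptom-free periods. Otherwise, declare the change in SAP 2.3.8.

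The cost is revised wording, one table and up to two model fits on data already collected. SAP section 1 leaves the plan open to change until database lock.

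### The protocol says it will investigate whether any statin excess of muscle symptoms lies in multiple sites; the SAP only describes site, bars a treatment comparison, and does not declare the change

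*SAP*

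**What the plan says.** Protocol 2.13 lists as its second secondary outcome "Site of muscle symptoms (single or multiple; head and neck/upper limbs/lower limbs/trunk"). Protocol 2.17, under secondary analyses, says what will be done with it: "We will investigate whether the excess muscle symptoms, if any, experienced during treatment periods with the IMP appears to be concentrated in multiple sites".

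The SAP retains site as a secondary outcome in sections 1.1 and 1.8. Its analysis appears only in 2.3.2, in the descriptive part, in three forms:

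- Over all symptomatic periods, where "the denominator will be the number of periods in which symptoms are experienced" and clustering within patient is ignored.
- The same again by treatment: "These descriptive statistics will be repeated splitting by treatment actually received".
- Per patient, through "a new location variable: always multiple sites/sometimes multiple sometimes single/always single site" and four ever/never indicators for body region.

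The passage closes by excluding any comparison: "Because these descriptive statistics do not respect the randomised allocation of treatment, no comparisons between treatment groups will be made". The next part of 2.3.2 sets out the randomised comparisons, and site is not among them. SAP 2.3.8 declares two changes from the protocol: removal of fixed period effects, and one added secondary analysis.

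**The concern.** The protocol sentence concerns an excess during IMP periods. That quantity is defined only by setting statin periods against placebo periods, so some contrast by treatment is needed to address it, even informally. The SAP offers none and expressly rules one out for the tables in which site appears.

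Two things are at stake. First, if statins do produce extra muscle symptoms, whether these are diffuse or localised is a question the trial said it would examine, and the final analysis would have nothing randomised to say about it. Second, a reader who relies on SAP 2.3.8 for the list of departures would conclude that the site analysis had survived.

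**Working it through.** The plan gives no figure for this analysis, so there is none to reproduce. The check is a comparison of texts, followed by a short illustration.

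**Step 1: does the protocol need a contrast?** Yes. The 2.17 sentence refers to an excess in IMP periods, and placebo periods are the only reference.

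**Step 2: does any SAP display supply it?**

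- All symptomatic periods pooled: no treatment dimension.
- By treatment actually received: there is a treatment dimension, but it is not the randomised one, the term is not defined, and the SAP forbids comparison.
- Patient-level variables: these pool each patient's statin and placebo periods, so no contrast can be recovered.

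**Step 3: is it restored elsewhere?** The randomised comparisons in 2.3.2 cover any muscle symptoms, symptoms attributed to study medication, an attribution-based version of the daily score, and the seven impact scores. The sensitivity analyses (2.3.4) and secondary analyses (2.3.7) do not mention site. Neither declared change in 2.3.8 concerns it.

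**Step 4: could the symptom-only table stand in?** Not by itself. Let p be the proportion of allocated periods with symptoms and m the multi-site share among symptomatic periods. Then

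- multi-site excess = p(statin) × m(statin) − p(placebo) × m(placebo)
- single-site excess = p(statin) × (1 − m(statin)) − p(placebo) × (1 − m(placebo))

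The documents give no values for p or m. All rates below are assumptions, chosen only to show the arithmetic.

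| Case | p: statin, placebo | m: statin, placebo | Multi-site per allocated period | Multi-site excess | Single-site excess |
|---|---|---|---|---|---|
| A | 50%, 40% | 60%, 50% | 30.0% v 20.0% | 10.0 points | 0.0 points |
| B | 50%, 40% | 50%, 50% | 25.0% v 20.0% | 5.0 points | 5.0 points |
| C | 50%, 30% | 45%, 60% | 22.5% v 18.0% | 4.5 points | 15.5 points |

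In B the shares among symptomatic periods are equal, yet there is a multi-site excess of 5 points. In C the share is lower on statin, while multi-site symptoms per allocated period are 4.5 points higher. The conditional share and the excess are different quantities. The protocol's question needs the second, which requires every allocated period in the denominator.

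**Step 5: is the needed method already in the SAP?** Yes. Sections 1.8 and 2.3.2 set the impact scores to zero in symptom-free periods, and the attributed-symptom outcome is also zero there. The same coding for multi-site symptoms removes the conditioning on a post-randomisation event, and a comparison by allocated treatment then respects the randomisation.

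**The case against.** The strongest reply is that little was promised. The protocol verb is investigate, the sentence is conditional on there being an excess, and no test, model or effect measure is given. In Protocol 2.13, the first and third secondary outcomes say that IMP periods will be compared with placebo; the site outcome does not. This stands: a reader might infer that a formal test was promised, and the documents do not support that. It does not dispose of the point, because the SAP bars even an informal comparison.

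The SAP's reason for barring it is also sound for the tables it chose, which condition on having symptoms. That is a reason for different tables, not for dropping the question.

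SAP 1.10 might be thought to fill the gap: "Periods of allocation to statin will be compared to periods of allocation to placebo, irrespective of adherence to the allocated treatment". It names no site variable and no model, and the specific text in 2.3.2 overrides it for site. Nor is the as-received table a clear breach of 1.10: the clause governs comparisons, and 2.3.2 says none is made. There is a tension in wording, no more.

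Three other readings are tempting and should be resisted:

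- That site is the only secondary outcome without a randomised estimate. Other symptoms attributed to the medication are also only described, and the decision on future statin use and the helpfulness of the result are not statin-placebo contrasts.
- That the as-received split would make the table point the wrong way because statin periods stopped for symptoms would leave the statin column. Treatment actually received is not defined, and a patient who took statin and then stopped did receive it. Neither the size nor the direction of any distortion can be derived.
- That the SAP describes site only by treatment received. That is one of three displays.

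**Conclusion.** The point holds as a gap between protocol and SAP. A stated protocol question that needs a statin-placebo contrast has no analysis in the SAP that could answer it, and the change is not declared. This is more than missing detail, because the SAP positively excludes the comparison.

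Its reach is limited to one exploratory question on one secondary outcome. The primary analysis and the planned randomised comparisons of any symptoms, attributed symptoms and impact scores are untouched. The conclusion rests on the texts alone; the assumed rates above show only why a symptom-only denominator does not give the excess. It should be put right before the SAP is finalised, which SAP section 1 allows up to database lock.

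**What to change.** In SAP 2.3.2, under the randomised comparisons:

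1. Add a per-period binary outcome: 1 if muscle symptoms are reported and recorded as more than one area on the patient questionnaire, otherwise 0, including periods with no symptoms. Compare allocated statin with allocated placebo using the logistic mixed model already specified for any muscle symptoms, with the 99% interval that SAP 1.10 sets for secondary outcomes. State in advance that the random treatment effect is dropped if the model does not converge.
2. Beside it, tabulate by allocated treatment the proportions of all periods with no, single-site and multi-site symptoms. A separate single-site odds ratio should not be read alone: it can fall simply because single-site pain has become multi-site, and would then look protective. The three-way table makes such a shift visible.
3. Split the descriptive site tables by allocated treatment, in addition to or in place of treatment actually received. If the latter stays, define it.
4. Record any remaining departure from Protocol 2.17 in SAP 2.3.8.

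The cost is a short SAP edit, one more model and one more table, using data the questionnaire already collects. There are two drawbacks. With at most six binary values per participant and an outcome no more common than any symptoms, precision will be limited, and the result should be labelled exploratory. The questionnaire (Protocol Appendix 4) asks for the area that hurts most and offers more than one area as an option, so it is an imperfect measure of multi-site symptoms; the report should say so.
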